#### 2.3.5. New lesions

The appearance of new malignant lesions denotes disease progression; therefore, some comments on detection of new lesions are important. There are no specific criteria for the identification of new radiographic lesions; however, the finding of a new lesion should be unequivocal: i.e. not attributable to differences in scanning technique, change in imaging modality or findings thought to represent something other than tumor (for example, some 'new' bone lesions may be simply healing or flare of pre-existing lesions). This is particularly important when the patient's baseline lesions show partial or complete response. For example, necrosis of a liver lesion may be reported on a CT scan report as a 'new' cystic lesion, which it is not.

A lesion identified on a follow-up study in an anatomical location that was not scanned at baseline is considered a new lesion and will indicate disease progression. An example of this is the patient who has visceral disease at baseline and while on study has a CT or MRI brain ordered which reveals metastases. The patient's brain metastases are considered to be evidence of PD even if he/she did not have brain imaging at baseline.

If a new lesion is equivocal, for example because of its small size, continued therapy and follow-up evaluation will clarify if it represents truly new disease. If repeat scans confirm there is definitely a new lesion, then progression should be declared using the date of the initial scan.

While FDG-PET response assessments need additional study, it is sometimes reasonable to incorporate the use of FDG-PET scanning to complement CT scanning in assessment of progression (particularly possible 'new' disease). New lesions on the basis of FDG-PET imaging can be identified according to the following algorithm:

- a. Negative FDG-PET at baseline, with a positive FDG-PET (=FDG avid with an uptake greater than twice that of the surrounding tissue on the attenuation corrected image) at follow-up is a sign of PD based on a new lesion.
- b. No FDG-PET at baseline and a positive FDG-PET at follow-up:
  - If the positive FDG-PET at follow-up corresponds to a new site of disease confirmed by CT, this is PD.
  - If the positive FDG-PET at follow-up is not confirmed as a new site of disease on CT, additional follow-up CT scans are needed to determine if there is truly progression occurring at that site (if so, the date of PD will be the date of the initial abnormal FDG-PET scan).
  - If the positive FDG-PET at follow-up corresponds to a pre-existing site of disease on CT that is not progressing on the basis of the anatomic images, this is not PD.

Confidential 79
December 31, 2019 Protocol Amendment 4

## 2.4. Evaluation of best overall response

The best overall response is the best response recorded from the start of the study treatment until the end of treatment taking into account any requirement for confirmation. On occasion a response may not be documented until after the end of therapy so protocols should be clear if post-treatment assessments are to be considered in determination of best overall response. Protocols must specify how any new therapy introduced before progression will affect best response designation. The patient's best overall response assignment will depend on the findings of both target and non-target disease and will also take into consideration the appearance of new lesions. Furthermore, depending on the nature of the study and the protocol requirements, it may also require confirmatory measurement (See Section 1.6). Specifically, in non-randomized trials where response is the primary endpoint, confirmation of PR or CR is needed to deem either one the 'best overall response'. This is described further below.

## 2.4.1. Time point response

It is assumed that at each protocol specified time point, a response assessment occurs. Table 1 provides a summary of the overall response status calculation at each time point for patients who have measurable disease at baseline.

When patients have non-measurable (therefore non-target) disease only, Table 2 is to be used.

Table 1: Criteria for Overall Response for Target (+/- Non-target) Disease

Target Lesions	Non-Target Lesions New Lesions		Overall Response
CR	CR No		CR
CR	Non-CR/Non PD No		PR
CR	Not evaluated No PR		PR
PR	Non-PD or not all evaluated No		PR
SD	Non-PD or not all evaluated No		SD
Not all evaluated	Non-PD No		NE
PD	Any Yes or No PD		PD
Any	PD	Yes or No	PD
Any	Any	Yes PD	
CR = complete response, PR= partial response, SD=stable disease, PD= progressive disease, NE=inevaluable			

Table 2: Criteria for Overall Response for Non-target Disease Only

Non-Target Lesions	New Lesions	Overall Response
CR	No	CR
Non-CR/non-PD	No	Non-CR/non-PD
Not all evaluated	No	NE

Unequivocal PD	Yes or No	PD	
Any	Yes	PD	
CR = complete response, PR= partial response, SD=stable disease, PD= progressive disease, NE=inevaluable			

## 2.4.2. Missing assessments and inevaluable designation

When no imaging/measurement is done at all at a particular time point, the patient is not evaluable (NE) at that time point. If only a subset of lesion measurements are made at an assessment, usually the case is also considered NE at that time point, unless a convincing argument can be made that the contribution of the individual missing lesion(s) would not change the assigned time point response. This would be most likely to happen in the case of PD. For example, if a patient had a baseline sum of 50mm with three measured lesions and at follow-up only two lesions were assessed, but those gave a sum of 80 mm, the patient will have achieved PD status, regardless of the contribution of the missing lesion.

## 2.4.3. Best overall response: all time points

The best overall response is determined once all the data for the patient is known.

Best response determination in trials where confirmation of complete or partial response IS NOT required: Best response in these trials is defined as the best response across all time points (for example, a patient who has SD at first assessment, PR at second assessment, and PD on last assessment has a best overall response of PR). When SD is believed to be best response, it must also meet the protocol specified minimum time from baseline. If the minimum time is not met when SD is otherwise the best time point response, the patient's best response depends on the subsequent assessments. For example, a patient who has SD at first assessment, PD at second and does not meet minimum duration for SD, will have a best response of PD. The same patient lost to follow-up after the first SD assessment would be considered inevaluable.

Best response determination in trials where confirmation of complete or partial response IS required: Complete or partial responses may be claimed only if the criteria for each are met at a subsequent time point as specified in the protocol (generally 4 weeks later). In this circumstance, the best overall response can be interpreted as in Table 3.

Table 3: Best Overall Response When Confirmation of CR and PR is Required

Overall Response First Time Point	Overall Response Subsequent Time Point	BEST Overall Response
CR	CR	CR
CR	PR	SD, PD, or PD a
CR	SD	SD provided minimum criteria for SD duration met, otherwise, PD
CR	PD	SD provided minimum criteria for SD duration met, otherwise, PD

Confidential
December 31, 2019

CR	NE	SD provided minimum criteria for SD duration met, otherwise, NE
PR	CR	PR
PR	PR	PR
PR	SD	SD
PR	PD	SD provided minimum criteria for SD duration met, otherwise, PD
PR	NE	SD provided minimum criteria for SD duration met, otherwise, NE
NE	NE	NE

CR = complete response, PR= partial response, SD=stable disease, PD= progressive disease, NE=inevaluable

aIf a CR is truly met at first time point, then any disease seen at a subsequent time point, even disease meeting PR criteria relative to baseline, makes the disease PD at that point (since disease must have reappeared after CR). Best response would depend on whether minimum duration for SD was met. However, sometimes 'CR' may be claimed when subsequent scans suggest small lesions were likely still present and, in fact, the patient had PR, not CR at the first time point. Under these circumstances, the original CR should be changed to PR, and the best response is PR.

## 2.4.4. Special notes on response assessment

When nodal disease is included in the sum of target lesions and the nodes decrease to 'normal' size (<10 mm), they may still have a measurement reported on scans. This measurement should be recorded even though the nodes are normal in order not to overstate progression should it be based on increase in size of the nodes. As noted earlier, this means that patients with CR may not have a total sum of 'zero' on the case report form (CRF).

In trials where confirmation of response is required, repeated 'NE' time point assessments may complicate best response determination. The analysis plan for the trial must address how missing data/assessments will be addressed in determination of response and progression. For example, in most trials it is reasonable to consider a patient with time point responses of PR-NE-PR as a confirmed response.

Patients with a global deterioration of health status requiring discontinuation of treatment without objective evidence of disease progression at that time should be reported as 'symptomatic deterioration'. Every effort should be made to document objective progression even after discontinuation of treatment. Symptomatic deterioration is not a descriptor of an objective response: it is a reason for stopping study therapy. The objective response status of such patients is to be determined by evaluation of target and non-target disease as shown in **Tables 1–3.** 

Conditions that define 'early progression, early death and inevaluability' are study specific and should be clearly described in each protocol (depending on treatment duration, treatment periodicity).

Confidential
December 31, 2019

In some circumstances, it may be difficult to distinguish residual disease from normal tissue. When the evaluation of complete response depends upon this determination, it is recommended that the residual lesion be investigated (fine needle aspirate/biopsy) before assigning a status of complete response. FDG-PET may be used to upgrade a response to a CR in a manner similar to a biopsy in cases where a residual radiographic abnormality is thought to represent fibrosis or scarring. The use of FDG-PET in this circumstance should be prospectively described in the protocol and supported by disease specific medical literature for the indication. However, it must be acknowledged that both approaches may lead to false positive CR due to limitations of FDG-PET and biopsy resolution/ sensitivity.

For equivocal findings of progression (e.g. very small and uncertain new lesions; cystic changes or necrosis in existing lesions), treatment may continue until the next scheduled assessment. If at the next scheduled assessment, progression is confirmed, the date of progression should be the earlier date when progression was suspected.

## 2.5. Frequency of tumor re-evaluation

Frequency of tumor re-evaluation while on treatment should be protocol specific and adapted to the type and schedule of treatment. However, in the context of phase II studies where the beneficial effect of therapy is not known, follow-up every 6–8 weeks (timed to coincide with the end of a cycle) is reasonable. Smaller or greater time intervals than these could be justified in specific regimens or circumstances. The protocol should specify which organ sites are to be evaluated at baseline (usually those most likely to be involved with metastatic disease for the tumor type under study) and how often evaluations are repeated. Normally, all target and non-target sites are evaluated at each assessment. In selected circumstances, certain non-target organs may be evaluated less frequently. For example, bone scans may need to be repeated only when complete response is identified in target disease or when progression in bone is suspected.

After the end of the treatment, the need for repetitive tumor evaluations depends on whether the trial has as a goal the response rate or the time to an event (progression/death). If 'time to an event' (e.g. time to progression, disease-free survival, progression-free survival) is the main endpoint of the study, then routine scheduled re-evaluation of protocol specified sites of disease is warranted. In randomized comparative trials in particular, the scheduled assessments should be performed as identified on a calendar schedule (for example: every 6–8 weeks on treatment or every 3–4 months after treatment) and should not be affected by delays in therapy, drug holidays or any other events that might lead to imbalance in a treatment arm in the timing of disease assessment.

#### 2.6. Confirmatory measurement/duration of response

## 2.6.1. Confirmation

In non-randomized trials where response is the primary endpoint, confirmation of PR and CR is required to ensure responses identified are not the result of measurement error. This will also permit appropriate interpretation of results in the context of historical data where response has traditionally required confirmation in such trials (see Bogaerts J, et al, Eur Jour Cancer,2009;45:248-260). However, in all other circumstances, i.e. in randomized trials (phase II or III) or studies where stable disease or progression are the primary endpoints, confirmation

Confidential 83
December 31, 2019 Protocol Amendment 4

of response is not required since it will not add value to the interpretation of trial results. However, elimination of the requirement for response confirmation may increase the importance of central review to protect against bias, in particular in studies which are not blinded.

In the case of SD, measurements must have met the SD criteria at least once after study entry at a minimum interval (in general not less than 6–8 weeks) that is defined in the study protocol.

## 2.6.2. Duration of overall response

The duration of overall response is measured from the time measurement criteria are first met for CR/PR (whichever is first recorded) until the first date that recurrent or progressive disease is objectively documented (taking as reference for progressive disease the smallest measurements recorded on study).

The duration of overall complete response is measured from the time measurement criteria are first met for CR until the first date that recurrent disease is objectively documented.

# 2.6.3. Duration of stable disease

Stable disease is measured from the start of the treatment (in randomized trials, from date of randomization) until the criteria for progression are met, taking as reference the smallest sum on study (if the baseline sum is the smallest, this is the reference for calculation of PD).

The clinical relevance of the duration of stable disease varies in different studies and diseases. If the proportion of patients achieving stable disease for a minimum period of time is an endpoint of importance in a particular trial, the protocol should specify the minimal time interval required between two measurements for determination of stable disease.

Note: The duration of response and stable disease as well as the progression-free survival are influenced by the frequency of follow-up after baseline evaluation. It is not in the scope of this guideline to define a standard follow-up frequency. The frequency should take into account many parameters including disease types and stages, treatment periodicity and standard practice. However, these limitations of the precision of the measured endpoint should be taken into account if comparisons between trials are to be made.

# 2.7. Progression-free survival/proportion progression-free

### 2.7.1. Phase II trials

This guideline is focused primarily on the use of objective response endpoints for phase II trials. In some circumstances, 'response rate' may not be the optimal method to assess the potential anticancer activity of new agents/regimens. In such cases 'progression-free survival' (PFS) or the 'proportion progression-free' at landmark time points, might be considered appropriate alternatives to provide an initial signal of biologic effect of new agents. It is clear, however, that in an uncontrolled trial, these measures are subject to criticism since an apparently promising observation may be related to biological factors such as patient selection and not the impact of the intervention. Thus, phase II screening trials utilizing these endpoints are best designed with a randomized control. Exceptions may exist where the behavior patterns of certain cancers are so consistent (and usually consistently poor), that a non-randomized trial

Confidential 84
December 31, 2019 Protocol Amendment 4

is justifiable. However, in these cases it will be essential to document with care the basis for estimating the expected PFS or proportion progression-free in the absence of a treatment effect.

#### 2.7.2. Phase III trials

Phase III trials in advanced cancers are increasingly designed to evaluate progression-free survival or time to progression as the primary outcome of interest. Assessment of progression is relatively straightforward if the protocol requires all patients to have measurable disease. However, restricting entry to this subset of patients is subject to criticism: it may result in a trial where the results are less likely to be generalizable if, in the disease under study, a substantial proportion of patients would be excluded. Moreover, the restriction to entry will slow recruitment to the study. Increasingly, therefore, trials allow entry of both patients with measurable disease as well as those with non-measurable disease only. In this circumstance, care must be taken to explicitly describe the findings which would qualify for progressive disease for those patients without measurable lesions. Furthermore, in this setting, protocols must indicate if the maximum number of recorded target lesions for those patients with measurable disease may be relaxed from five to three. As found in the 'special notes on assessment of progression', these guidelines offer recommendations for assessment of progression in this setting. Furthermore, if available, validated tumor marker measures of progression (as has been proposed for ovarian cancer) may be useful to integrate into the definition of progression. Centralized blinded review of imaging studies or of source imaging reports to verify 'unequivocal progression' may be needed if important drug development or drug approval decisions are to be based on the study outcome. Finally, as noted earlier, because the date of progression is subject to ascertainment bias, timing of investigations in study arms should be the same.

Confidential 85
December 31, 2019 Protocol Amendment 4

# APPENDIX F. RESPONSE ASSESSMENT IN NEURO-ONCOLOGY BRAIN METASTASES (RANO-BM)

Before the RANO brain metastases (RANO-BM) working group convened in 2011, clinical trials of patients with brain metastases were notable for their heterogeneity with respect to patient population, imaging modality, frequency of assessment, definitions of progression, and response (WHO versus modified Macdonald Criteria versus RECIST 1.1 versus ad hoc radiographic assessment criteria), among other features. Even though BMs are the most common malignant brain tumor, affecting up to one third of adults with cancer, the field lacked the common definitions and guidelines for response assessment and clinical trial design that are needed for quality and consistency in trial reporting. RANO-BM proposed response assessment on the basis of literature review and consensus opinion. For clinical trials of systemic agents, the group recommended the use of RECIST 1.1 for non-CNS response assessment and RANO-BM for CNS response assessment. With features that were adopted from RECIST and RANO-high grade gliomas (RANO-HGG) to meet the particular needs of patients with solid tumor brain metastases, RANO-BM response assessment is based on the sum diameter of one-dimensional measurements, corticosteroid dosing, and clinical status (see Table 1 below). Guidance is also provided for cases in which patients were treated with stereotactic radiosurgery or immunotherapy to avoid equating treatment effect with tumor progression.

Several controversies arose during the development of these criteria. As a result of concerns over reproducibility and the interpretation of changes in small lesions as well as to maintain consistency with RECIST 1.1, measurable disease was defined in RANO-BM as a contrast-enhancing lesion that can be accurately measured in at least one dimension with a minimum size of 10 mm. The working group acknowledged that many patients present with subcentimeter brain metastases and, therefore, RANO-BM provides guidance for investigators who choose to lower the minimum size limit of measurable disease to 5 mm. Similarly, the use of one-dimensional versus volumetric assessments was debated within the working group. Ultimately, one dimensional measurements formed the basis of RANO-BM criteria as the group felt that the existing data on volumetric assessments were not strong enough to justify the real-time cost and complexity as for RANO-HGG. However, RANO-BM does provide guidance for those investigators who wish to include volumetric assessment within their trials.

Table 1. Neuro-Oncology Response Criteria for Brain Metastases

Criterion	CR	PR	SD	PD
Target lesions	None	≥ 30% decrease in sum LD relative to baseline	< 30% decrease relative to baseline but < 20% increase in sum LD relative to nadir	≥ 20% increase in sum LD relative to nadir*
Nontarget lesions	None	Stable or improved	Stable or improved	Unequivocal PD*
New lesion(s)†	None	None	None	Present*
Corticosteroids	None	Stable or decreased	Stable or decreased	NA‡
Clinical status	Stable or improved	Stable or improved	Stable or improved	Worse*
Requirement for response	All	All	All	Any‡

NOTE. Reprinted from Lin et al, with permission from Elsevier. (Lin NU, Lee EQ, Aoyama H, et al: Response assessment criteria for brain metastases: Proposal from the RANO group. Lancet Oncol 16:e270-e278, 2015)

Abbreviations: CR, complete response; LD, longest dimension; NA, not applicable; PD, progressive disease; PR, partial response; SD, stable disease.

†New lesion = new lesion not present on prior scans and visible in at least two projections. If a new lesion is equivocal, for example, because of its small size, continued therapy may be considered and follow-up evaluation will clarify whether it represents truly new disease. If repeat scans confirm there is definitely a new lesion, then progression should be declared using the date of the initial scan showing the new lesion. For immunotherapy-based approaches, new lesions alone do not define progression.

‡Increase in corticosteroids alone will not be taken into account in determining progression in the absence of persistent clinical deterioration.

\*Progression occurs when this criterion is met.

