Blood for hematology and serum chemistry determinations will be collected within 28 days of Cycle 1 Day 1 and on Day 1 of each cycle and at the End of Treatment Visit.

ECGs will be taken within 28 days prior to Cycle 1 Day 1, pre-infusion and 5 minutes following the end of the E6201 2-hour infusion, on Day 1 of every cycle thereafter, and at the End-of-Study visit.

CNS and non-CNS systemic disease assessments will be based on magnetic resonance image (MRI) or computed tomography (CT) if unable to perform MRI for intracranial disease. Assessments will be obtained at Week 8 and every 8 weeks thereafter until documented progression of disease (PD). Subjects who demonstrate clinical benefit will be allowed to continue therapy until progression of disease, observation of unacceptable adverse events, intercurrent illness or changes in the subject's condition that prevents further study participation.

Safety will be assessed through the monitoring of adverse events (AEs), clinical laboratory parameters (hematology and serum chemistry), vital sign measurements, ECGs and physical examinations. Adverse events will be classified according to the Medical Dictionary for Regulatory Affairs (MedDRA) and graded according to the National Cancer Institute Common Terminology Criteria for Adverse Events (NCI CTCAE) version 4.03.

Efficacy assessments will be determined on the basis of MRI and/or CT scans with best treatment response at any protocol-specified time point for intracranial disease, duration of response, duration of stable disease, and time to CNS metastasis disease progression based on RECIST v.1.1 and RANO-BM. Response rates also will be determined for non-CNS systemic disease. Progression-free survival (PFS) and overall survival (OS) will be evaluated.

A correlation will be made between *BRAF* mutational status (e.g., type, heterozygosity or homozygosity) in archival tissue with clinical outcome.

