#### 6. STUDY POPULATION

#### 6.1. Subject Inclusion Criteria

Subjects must meet all of the following criteria to participate in the study:

- Males and females  $\geq$  18 years of age
- Histologically or cytologically confirmed Stage IV metastatic *BRAF* V600-mutated melanoma
- Documented metastasis of the primary tumor to the CNS
- *BRAF*-mutation melanoma tumor status will be established prior to entry based on previous *BRAF*-gene analysis reports from a CLIA qualified laboratory. If a report is not available, the mutation analysis will be performed at Screening on archival tissue.
- Other metastatic melanoma systemic disease allowed
- At least one measurable brain metastasis 0.5 3.0 cm, as assessed by MRI  $\leq$  3 weeks prior to initiation of study treatment, and does not require immediate local intervention (surgery or radiosurgery)
- Prior stereotactic radiosurgery and/or excision of up to 3 brain metastases is allowed > 3
  weeks before initiation of study treatment, provided neurological sequelae have resolved
  completely and at least one measurable metastasis with documented disease progression is
  present on MRI
- One prior line of immunotherapy for metastatic disease is allowed, if  $\geq 2$  weeks has elapsed between the end of therapy and initiation of study treatment
- Prior melanoma adjuvant immunotherapy is allowed, if  $\geq 6$  months has elapsed between the end of therapy and initiation of study treatment
- Prior melanoma adjuvant BRAF/MEK inhibitor treatment is allowed if  $\geq 12$  months has elapsed between the end of therapy and initiation of study treatment
- Able to swallow and retain oral medication with no clinically significant gastrointestinal abnormalities that may alter absorption, such as malabsorption syndrome or major resection of the stomach or bowels (Combination Safety Run-in and Expansion Phases of the study only)
- Asymptomatic or symptomatic CNS metastasis is allowed
- Stable dose of corticosteroids for CNS metastasis for  $\geq 7$  days is allowed
- Patients with seizures due to CNS metastases must be controlled with stable anti-epileptic treatment for ≥ 14 days
- Bisphosphonates and/or denosumab are allowed
- Adequate performance status: Eastern Cooperative Oncology Group (ECOG) ≤ 2 (APPENDIX A)
- Life expectancy of  $\geq 3$  months
- Adequate hematologic parameters without ongoing transfusional support:
  - Hemoglobin (Hb)  $\geq$  9 g/dL

Confidential 39
December 31, 2019 Protocol Amendment 4

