## 2.3.1. Evaluation of target lesions

Complete Response (CR): Disappearance of all target lesions. Any pathological lymph nodes (whether target or non-target) must have reduction in short axis to <10 mm.

Partial Response (PR): At least a 30% decrease in the sum of diameters of target lesions, taking as reference the baseline sum diameters.

Progressive Disease (PD): At least a 20% increase in the sum of diameters of target lesions, taking as reference the smallest sum on study (this includes the baseline sum if that is the smallest on study). In addition to the relative increase of 20%, the sum must also demonstrate an absolute increase of at least 5 mm. (Note: the appearance of one or more new lesions is also considered progression).

Stable Disease (SD): Neither sufficient shrinkage to qualify for PR nor sufficient increase to qualify for PD, taking as reference the smallest sum diameters while on study.

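### Appendix F scores CNS progression on a 20% rise in the lesion sum with no minimum growth in millimetres, whereas Appendix E also requires 5 mm, so the two size rules disagree for every nadir sum below 25 mm.

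*Combined protocol and SAP*

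**What the plan says.** Section 5.1 and Section 10.4.1.1 have CNS disease assessed by both RECIST 1.1 (Appendix E) and RANO-BM (Appendix F). Section 5.1 lists among the efficacy assessments "time to CNS metastasis disease progression based on RECIST v.1.1 and RANO-BM".

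- **Appendix F, Table 1.** The target-lesion cell for progression reads "≥ 20% increase in sum LD relative to nadir". Its asterisk leads to the footnote "Progression occurs when this criterion is met". No footnote adds a minimum in millimetres. The stable-disease cell requires a rise of less than 20%, so a 20% rise cannot be stable disease.
- **Appendix E, Section 2.3.1.** Progression is "At least a 20% increase in the sum of diameters of target lesions, taking as reference the smallest sum on study", followed by "In addition to the relative increase of 20%, the sum must also demonstrate an absolute increase of at least 5 mm".
- **Section 6.1.** Entry requires "At least one measurable brain metastasis 0.5" to 3.0 cm by MRI.
- **Appendix E, Sections 1.1.1 and 1.1.2.** Lesions under 10 mm are non-measurable.
- **Appendix F, narrative text.** Measurable disease is set at 10 mm, partly because changes in small lesions are hard to reproduce. It mentions guidance for lowering the limit to 5 mm but does not reproduce it.

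**The concern.** Appendix F is not background reading. Section 10.4.1.1 refers to it as an operative definition. Read as printed, it lets a very small change in a very small lesion count as CNS progression. Because the reference is the nadir, the problem grows after a response. A 5 mm lesion that shrinks to 3.5 mm has met the 30% threshold for partial response; a rise of 0.7 mm, to 4.2 mm, then meets the progression cell while the lesion is still below its baseline size.

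Duration of intracranial response, duration of stable disease and time to CNS progression all end at intracranial progression (Sections 10.4.1.2 and 11.3.2.2). Scans continue only until documented progression (Section 5.1), so a false call also ends observation. With 18 subjects planned for the main analysis, a few false progressions could visibly move a Kaplan-Meier median. Where the two criteria disagree about the same scan, the protocol gives no rule for choosing the date.

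**Working it through.** The plan states no figure for this point, so there is nothing to reproduce first. The check compares the two printed rules and then asks how often each would fire on a lesion that has not changed.

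**1. Rise needed from nadir sum S**

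Appendix F: 0.20 × S. Appendix E: the larger of 0.20 × S and 5 mm. They coincide at S = 5 / 0.20 = 25 mm.

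| Nadir sum (mm) | Appendix F (mm) | Appendix E size rule (mm) |
|---|---|---|
| 5 | 1 | 5 |
| 10 | 2 | 5 |
| 15 | 3 | 5 |
| 20 | 4 | 5 |
| 25 | 5 | 5 |

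A 1 mm rise is enough only when S is 5 mm or less (1/5 = 20%; 1/6 = 16.7%; 1/10 = 10%). Two 5 mm lesions need 2 mm in total.

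**2. False progression at one follow-up scan**

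Assume independent normal reading errors with SD s per lesion. The documents give no value, so s = 0.25, 0.5 and 1.0 mm are assumptions. Let the true, unchanged sum be T, the baseline reading Y0 and the follow-up reading Y1. Appendix F fires when Y1 ≥ 1.2 × Y0. The quantity Y1 − 1.2 × Y0 has mean −0.2T and SD s × √(1 + 1.44) = s × √2.44, so

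P = 1 − Φ(0.2T / (s√2.44)).

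Single 5 mm lesion: z = 2.56, 1.28 and 0.64, giving P = 0.5%, 10% and 26%.

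For two 5 mm lesions (T = 10 mm), replace s by s√2. At s = 0.5 and 1.0 mm, P = 3.5% and 18%.

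**3. False progression over three follow-up scans, against the running nadir**

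Simulated with 400,000 subjects per setting:

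| Unchanged target disease | s = 0.25 mm | s = 0.5 mm | s = 1.0 mm | With a 5 mm minimum |
|---|---|---|---|---|
| One 5 mm lesion | 2.7% | 37% | 72% | about 0.1% or less |
| One 10 mm lesion | about 0% | 2.7% | 37% | about 0.1% or less |
| One 20 mm lesion | about 0% | about 0% | 2.7% | about 0.1% or less |

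For two 5 mm lesions at s = 1.0 mm, the three-scan risk is 58% under Appendix F and 3.2% with a 5 mm minimum.

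**4. Sensitivity to entry selection**

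A lesion whose true size is 5 mm enters only if it is read at 5 mm or more, which tends to raise the baseline reading. Conditioning on that, for s = 0.5 to 1.0 mm, the single-scan risk is 0.5% to about 5% and the three-scan risk is 24% to 57%. The first comparison is much safer, but the three-scan risk stays large because later readings can set a low nadir.

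**5. Does anything else in the protocol close the gap?**

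The equivocal-finding footnote in Appendix F covers new lesions only. The equivocal-progression rule in Appendix E, Section 2.4.4, belongs to RECIST. Section 7.1.1 speaks of confirmed progression but defines no procedure for target-lesion growth.

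**The case against.** The best counter-argument is that the alarming example lies at the edge of the eligible range and that its size is assumed. Much of this stands. Eligible lesions run to 3.0 cm, the documents give no size distribution, and from a 25 mm sum upward the rules are identical. At a reading SD of 0.25 mm the risk is small even at 5 mm. The affected endpoints are descriptive medians in a single arm.

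Several stronger readings are tempting, and the documents do not support them:

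- A reader might infer that a 1 mm reading difference is generally CNS progression in this trial. That holds only when the nadir sum is 5 mm or less, and only under Appendix F.
- A reader might infer that Appendix E's 5 mm rule makes a lone 5 mm lesion read at 6 mm stable disease. Under Appendix E that lesion is non-measurable. No target sum exists, the 5 mm rule is never reached, and the result, absent new lesions or unequivocal growth, is Non-CR/non-PD (Appendix E, Section 2.4.1, Table 2).
- A reader might infer that PFS and the primary endpoint are directly distorted. Section 5.1 ties RANO-BM to the intracranial endpoints and lists PFS separately, and the thresholds for complete and partial response are unchanged. A later response lost to an early false progression is possible but cannot be sized from the documents.
- A reader might infer that the published RANO-BM criteria lack a millimetre threshold. The protocol mentions guidance for 5 mm lesions without reproducing it. The point concerns what this protocol prints and instructs.

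The objection does not remove the conflict. The table as printed is what the protocol tells readers to apply, and it departs from Appendix E over much of the eligible size range.

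**Conclusion.** The point holds in this form: the Appendix F progression cell has no absolute minimum, Appendix E has 5 mm, the size rules disagree below a nadir sum of 25 mm, and eligibility admits lesions from 0.5 cm that Appendix E does not treat as measurable. The disagreement in thresholds is arithmetic and needs no assumption.

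The false-progression rates depend on the assumed reading SD, on independent normal errors, and on how many subjects have small target sums, which is unknown. At 5 mm the three-scan risk therefore ranges from minor to dominant. The endpoints at risk are duration of intracranial response, duration of stable disease and time to CNS progression, plus PFS wherever CNS progression is scored by RANO-BM. This should be corrected before the progression endpoints are scored; it does not undermine the response-rate definition.

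**What to change.** For scoring the CNS progression endpoints, amend the target-lesion progression cell in Appendix F Table 1 so that it requires both the 20% rise from nadir and an absolute increase of at least 5 mm, as in Appendix E, Section 2.3.1. Adjust the stable-disease cell to match. Leave new lesions, unequivocal non-target progression and worse clinical status as they are.

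Reconcile Section 6.1, Appendix E (Sections 1.1.1, 1.1.2 and 2.3.1) and Appendix F on the smallest lesion that may be a target, and state which one criterion dates CNS progression.

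The edit is small. Its downside is that true growth confined to very small target lesions may be dated later: a single 5 mm lesion would have to reach 10 mm to progress on size alone, although the other progression criteria would still apply.

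Section 5.1 continues therapy until progression and Section 7.1.1 until confirmation of progression. Whether and how endpoint scoring bears on stopping treatment is for the sponsor to reconcile across those sections. No treatment-stopping rule is proposed here.
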